3.2 Start of study and end of study definitions

The start of the study is defined as the date the first enrolled subject signs an informed consent form (ICF). The end of the study is defined as the date of the last subject's last assessment (scheduled or unscheduled).

3.3 Selection of doses in the study

In the Phase 1 study in healthy volunteers and FSHD subjects (Study FIS-001-2018), the dose levels of 7.5 mg and 15 mg given by mouth BID with food were based on predictive nonclinical efficacy and published clinical target engagement and safety data for losmapimod previously

Fulcrum Therapeutics
Protocol FIS-001-2020

Losmapimod

generated by GSK. This Phase 1 study was recently completed and demonstrated that the 15 mg PO BID dose gives higher plasma levels and greater and more sustained target engagement in blood and tissues than the 7.5 mg PO BID dose, while resulting in similar safety and tolerability. The 15 mg BID dose is used in the ongoing Phase 2 studies in FSHD (Study FIS-001-2019 and Study FIS-002-2019). Prior results indicated the favorable safety and tolerability of losmapimod for chronic administration in the clinic, including in the context of severe acute diseases, such as acute myocardial infarction, in older people.

Prior studies of biodistribution of radiolabeled losmapimod by GSK showed ample distribution to all tissues including the lungs and the heart. Our recent target engagement data in the FSHD Phase 1 Study FIS-001-2018 indicates that p38²⁷ inhibition in blood, an assessment of p38 target engagement, is nearing a plateau at a losmapimod dose of 15 mg BID (see [Investigator Brochure](#) [Fulcrum Therapeutics 2020]), so doses of losmapimod higher than 15 mg PO BID are not warranted.

Additionally, at the proposed dose level of 15 mg PO BID, exposures are not expected to exceed those previously demonstrated to be safe in humans in multiple previous studies by GSK in healthy volunteers and various patient populations including older subjects ([Cherian et al 2011](#); [Barbour et al 2013](#); [Watz et al 2014](#); [Pascoe et al 2017](#)).

In previous clinical studies performed by GSK, it was shown that losmapimod significantly reduced markers of acute inflammation, including IL-6, CRP, and the CXCL13 chemokine after a single dose. Additionally, losmapimod reduced IL-6 after 15 days of treatment (GSK study RA3103718) and CRP acutely in subjects with acute myocardial infarction treated with 7.5 mg PO BID ([O'Donoghue et al 2016](#)). In subjects with COPD, losmapimod at 15 mg PO BID significantly reduced CRP over 12 weeks compared with placebo (GSK Study MKI 113006). In one study in healthy older adult volunteers, it was shown that a 15 mg PO BID dose of losmapimod for 4 days restored the normal immune response to varicella-zoster virus antigen challenge ([Vukmanovic-Stejic et al 2018](#)). The same formulation used in these previous clinical studies is the one proposed for use in the present clinical study.

The rationale for the proposed study duration of up to 28 days is that in most cases of COVID-19 the disease has resolved or resulted in severe outcomes over the first month from onset of symptoms. COVID-19 is a severe and rapidly progressive infection, especially in the high-risk population selected for the proposed Phase 3 trial. Therefore, treatment for longer than 14 days and study duration for longer than 28 days is not justified.

3.4 Study drug modifications and withdrawal

3.4.1 Dose modifications

Before trial medication is administered, changes in the subject's health status, including laboratory results if applicable, since the previous visit or previous dose should be checked.

Study drug interruptions and reductions are not permitted; subjects who are on dialysis may require a dose adjustment.

Study treatment dose adjustment for subjects on dialysis

The elimination of losmapimod is almost exclusively by metabolism, with only 2% of the administered dose recovered as unchanged drug in urine and feces. The metabolite is clinically inactive and does not exert any toxic effects.

Losmapimod has not been studied in renal insufficiency or renal failure. There has been 1 study of losmapimod in 17 subjects with focal segmental glomerulosclerosis (FSGS; FSG117283). In this study, subjects were given losmapimod 7.5 mg BID for 2 weeks followed by losmapimod 15 mg BID

Fulcrum Therapeutics
Protocol FIS-001-2020

Losmapimod

for 22 weeks. The mean duration of exposure to investigational product in subjects with FSGS was approximately 21 weeks (range: 3.7, 25 weeks).

Creatine and GFR for the population enrolled is in the table below.

Parameter	Mean (SD)	Range
eGFR (mL/min/1.73m ²)	79.4 (34.9)	36, 155
Creatine (μmol/L)	1.1 (0.5)	0.48, 2.07

eGFR = estimated glomerular filtration rate.

Losmapimod plasma concentration data in subjects with FSGS were compared with historical data obtained in the Phase 3 clinical trial in subjects with ACS. In general, exposure in subjects with FSGS was similar to subjects with ACS over the 24-week treatment period.

Consistent with the safety database of over 3500 subjects, the 2 most frequently reported AEs in the FSGS trial were headache (5/17; 29%) and fatigue (4/17; 24%). Seven AEs (by preferred term: vomiting, dizziness, oropharyngeal pain, nausea, blood creatinine increased, muscle spasms, and rash) were reported in 3 subjects (18%) each. All other AEs (by preferred term) were reported in ≤2 subjects each. Four subjects had at least 1 AE that led to withdrawal from the study or from treatment. The AEs that led to discontinuation were increase in blood urea nitrogen (related), increase in creatinine (not related), increase in cystatin C (related), and joint stiffness (related). None of the AEs was serious or severe; 3 of the AEs in 2 subjects were reported as related to study treatment.

Based on the current safety and exposure information, dosing adjustment is likely not needed for subjects with renal insufficiency. However, close monitoring of pharmacokinetics (PK) for such cases will be implemented to ensure that therapeutic concentrations are maintained (refer to **Section 6.2**). For those subjects requiring dialysis, dose adjustment may be needed and will be determined by pre- and post-dialysis PK by the DMC. Adjustments may be recommended by the DMC also for subjects on placebo who develop acute renal failure to prevent unblinding at the sites.

Study treatment discontinuation

Discontinuation of study treatment should be considered if:

- ALT or AST >8 x the upper limit of normal (ULN)
- ALT or AST >5 x ULN for more than 2 weeks
- ALT or AST >3 x ULN and (total bilirubin >2 x ULN or international normalized ratio >1.5) in the absence of reasonable alternative etiology
- ALT or AST >3 x ULN with the appearance of fatigue, nausea, vomiting, right upper quadrant pain or tenderness, fever, rash, and/or eosinophilia (>5%)
- QTcF prolongation with QTcF >500 msec or an increase in QTcF of >60 msec over baseline (confirmed by 2 successive repeat measurements)

In addition, the investigator must permanently discontinue the study drug if continued administration of the study drug is believed to be contrary to the best interests of the subject. The premature discontinuation of study drug might be triggered by an adverse event (AE), a diagnostic or therapeutic procedure, an abnormal assessment (eg, ECG or laboratory abnormalities), pregnancy, or for administrative reasons, in particular noncompliance with the protocol or withdrawal of the subject's consent. The reason for study drug interruption or premature discontinuation must be clearly documented in the eCRF.

Fulcrum Therapeutics
Protocol FIS-001-2020

Losmapimod

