⁷ Viral load testing will be collected daily for the first 4 days using central testing in the first 10 enrolled subjects as part of the sentinel safety assessment at select sites. For all subjects, including the sentinel subjects, swabs, saliva, or other sample collection (as specified in the Study Manual) for central viral load testing will be collected on D1 pretreatment and on D7 or earlier if being discharged from the hospital prior to D7.

MD

Medical Director, LOSVID Trial
Fulcrum Therapeutics, Inc.

[figure not shown]

Protocol FIS-001-2020

Clarification Memo – Eligibility Screening Labs

Date: 05 January 2021

The labs used to determine eligibility at screening should ideally be drawn after the informed consent form (ICF) has been signed and within 3 days of baseline on D1. This is to assure that the patient's current clinical status is known at screening. However, if patients are hospitalized and have had labs drawn prior to formal screening and the signing of the ICF and the Principal Investigator believes that they are representative of the patient's current clinical status, those labs can be used for screening purposes as long as they were obtained no more than 72 hours prior to D1. The labs need to have been drawn at the facility where the patient has been hospitalized continuously since the labs were drawn. This accommodation is intended to avoid unnecessary procedures on vulnerable patients while also minimizing interactions with hospital staff in an attempt to avoid the spread of infection.

[Redacted] MD
Medical Director, LOSVID Trial
Fulcrum Therapeutics, Inc.

Fulcrum Therapeutics
Protocol FIS-001-2020 – Summary of changes

Losmapimod

Summary of Changes to the Protocol

Protocol History	
Version and Date of Protocol	Comments

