4.2 Exclusion criteria

1. Inability to take oral medication at screening or baseline visit.
2. Evidence at screening or baseline of critical COVID-19 disease (eg, cardiac failure, septic shock or ARDS) or immediate need for intubation or mechanical ventilation per the judgment of the investigator.
3. Positive pregnancy test at screening for women of childbearing potential.
4. Lactating female at baseline for women of childbearing potential.
 - a. Note: a female will be considered eligible who is lactating at screening if she agrees to discontinue breastfeeding for the duration of the trial plus 14 days post last dose.
5. $\geq 5 \times$ upper limit of normal (ULN) for alanine or aspartate aminotransferases or total bilirubin $>1.5 \times$ ULN at screening or known history of Child-Pugh Class C, hepatitis B or C, or poorly controlled HIV infection. (Subjects with HIV infection who have normal CD4 counts may participate if they have been on a stable antiviral regimen for the 30 days prior to screening and are anticipated to remain on the regimen throughout the duration of the study.)
6. Glomerular filtration rate $<30 \text{ mL/min/1.73 m}^2$ at screening.
7. QTcF $>450 \text{ msec}$ for male or $>470 \text{ msec}$ for females or evidence of cardiac dysrhythmia at screening.
8. Significant history or evidence of clinically significant disorder, condition, current illness, illicit drug or other addiction, or disease that, in the opinion of the Investigator, would pose a risk to subject safety or interfere with the study evaluation, procedures, or completion.
9. Has been treated with immunomodulators or immunosuppressants including, but not limited to, interleukin (IL)-6 inhibitors, tumor necrosis factor (TNF) inhibitors, anti-IL-1 agents, and Janus kinase inhibitors, within 5 half-lives or 30 days, whichever is longer, prior to randomization, or plan to receive these agents any time during the study period.
10. Treatment with hydroxychloroquine/ chloroquine in the past 30 days or plan to receive these agents as part of investigational clinical trials or SOC any time during the study period.
11. Recent (within 30 days) or current participation in other COVID-19 therapeutic trials or expanded access programs.
12. Prior or current participation in COVID-19 vaccine trials.

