5 INVESTIGATIONAL MEDICINAL PRODUCT

5.1 Investigational drug and matching placebo

Losmapimod will be provided in tablets of 7.5 mg for oral administration.

Matching placebo tablets will be provided for oral administration.

The tablets are plain white, round, biconvex, film-coated tablets. The proposed dosing regimen is as a twice daily dose of 15 mg (2 x 7.5 mg tablets/dose BID). The proposed duration of treatment is for up to 14 days.

Subjects should take their dose of losmapimod or placebo with food whenever possible and with 240 mL of room temperature water.

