Study drug should be discontinued for subjects who meet the QTc prolongation criteria as a result of within-protocol specific testing or unscheduled testing (see [Section 3.4.4](#) stopping criteria). This AESI must be reported to the sponsor within 24 hours of awareness per the SAE reporting procedures ([Section 7.1.6](#)). Further safety steps should be taken to closely observe and follow-up the event until resolution and treatment initiated per local standard of care.

Adverse event of special interest: Drug-induced liver injury

The following 3 laboratory value criteria must be met for potential DILI, or "Hy's Law":

- An elevated alanine transaminase or aspartate transaminase laboratory value that is $\geq 3 \times$ ULN
- An elevated total bilirubin laboratory value that is $\geq 2 \times$ ULN
- An alkaline phosphatase laboratory value that is $< 2 \times$ ULN

Study drug should be discontinued for subjects who meet the laboratory criteria for potential DILI as a result of within-protocol specific testing or unscheduled testing (see [Section 3.4.4](#) stopping criteria). This AESI must be reported to the sponsor within 24 hours of awareness per the SAE reporting procedures ([Section 7.1.6](#)). Further safety steps should be taken to closely observe and follow-up the event until resolution. These steps include, but are not limited to:

- Making every reasonable attempt to have the subject return to the clinic within 24 hours for repeat liver tests
- Obtaining a more detailed history of symptoms and prior or concurrent disease, concomitant medication use, alcohol use, recreational drug use, and special diets
- Repeating liver enzyme and serum bilirubin tests twice weekly. Frequency of retesting can decrease to once a week or less if abnormalities stabilize and the subject is asymptomatic
- Obtaining viral hepatitis serology
- Considering liver imaging and/or hepatology consultation

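### The advisory liver criterion of ALT or AST above 5 x ULN for over two weeks cannot be met within a 14-day course by a rise that begins on drug (minor; cheap to fix)

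*Protocol*

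**What the plan says.** Protocol Section 3.4.1 gives four liver findings for which stopping study drug should be considered:

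1. ALT or AST above 8 x ULN.
2. "ALT or AST >5 x ULN for more than 2 weeks".
3. ALT or AST above 3 x ULN with bilirubin above 2 x ULN or INR above 1.5, when no other reasonable cause is present.
4. ALT or AST above 3 x ULN with newly appearing symptoms, fever, rash or eosinophilia.

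The QTcF entry in the same list asks for a finding "confirmed by 2 successive repeat measurements". The section then adds a mandatory clause on the subject's behalf: "the investigator must permanently discontinue the study drug if continued administration of the study drug is believed to be contrary to the best interests". It names laboratory abnormalities among the possible triggers.

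Section 7.1.8 treats drug-induced liver injury (DILI) as an event of special interest: "Study drug should be discontinued for subjects who meet the laboratory criteria for potential DILI". Those criteria need ALT or AST of at least 3 x ULN, bilirubin of at least 2 x ULN and alkaline phosphatase below 2 x ULN, all together.

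On duration, Section 5.1 states: "The proposed duration of treatment is for up to 14 days". Section 3.3 adds that "treatment for longer than 14 days and study duration for longer than 28 days is not justified". Section 3.4.1 does not permit interruptions.

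On entry, exclusion criterion 5 (Section 4.2) removes subjects at or above five times the "upper limit of normal (ULN) for alanine or aspartate aminotransferases or total bilirubin" above 1.5 x ULN, both at screening. The January 2021 clarification memo lets sites use earlier hospital results: "those labs can be used for screening purposes as long as they were obtained no more than 72 hours prior to D1".

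**The concern.** A duration of more than two weeks suits a chronic-dosing study. Here the whole course is two weeks, so by the time a rise that began on drug has lasted long enough, there is no drug left to stop. The protocol evidently meant to have a prompt at 5 x ULN, since it lists one and treats liver injury as an event of special interest.

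At stake is a subject who goes from 1 to 7 x ULN on treatment without symptoms and with bilirubin below 2 x ULN. That subject meets no listed numeric criterion while dosing continues, and sites have no common number between 5 and 8 x ULN to act on. Because dose holds are barred, the choice is to continue or to stop for good, so a usable prompt has some value.

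**Working it through.** **Check of the timeline.** Section 3.1 gives a maximum participation of 34 days. Three screening days + 14 treatment days + 14 follow-up days + a 3-day window = 34, which agrees with a 14-day course.

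**Rise that begins on drug.** 28 doses have 27 intervals of 0.5 day: 27 x 0.5 = 13.5 days from first to last dose, against more than 14 required. In whole days:

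| Rise starts or is first seen | Days elapsed by Day 14 | First day beyond 14 days |
|---|---|---|
| Day 1 | 13 | Day 16 |
| Day 2 | 12 | Day 17 |
| Day 4 | 10 | Day 19 |
| Day 7 | 7 | Day 22 |

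**Rise that begins before dosing.** An eligible subject was below 5 x ULN on a screening sample at most 72 hours old. The longest possible time above 5 x ULN up to the last dose is 3 + 13.5 = 16.5 days, so the criterion can be met on drug for at most 16.5 - 14 = 2.5 days. The first scheduled draw after screening is Day 1, and Day 1 to Day 14 is 13 days. Scheduled draws alone therefore cannot document it, though routine-care results entered in the eCRF might.

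**Do the other criteria cover it?** Take ALT 7 x ULN, no symptoms or eosinophilia, bilirubin below 2 x ULN, no INR rise. Criterion 1 needs above 8. Criterion 3 needs bilirubin above 2 x ULN or INR above 1.5. Criterion 4 needs symptoms, fever, rash or eosinophilia. The DILI rule needs bilirubin of at least 2 x ULN. None is met.

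**What a confirmed 5 x ULN prompt would leave to prevent.** Chemistry draws after Day 1 fall on Days 2, 4, 7, 10 and 14 (Administrative Letter table). Doses still ahead after confirmation on Day c = 2 x (14 - c).

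| First seen | Confirmed | Doses ahead |
|---|---|---|
| Day 2 | Day 4, scheduled | 20 |
| Day 4 | Day 7, scheduled | 14 |
| Day 7 | Day 10, scheduled | 8 |
| Day 10 | Day 14, scheduled | 0 |
| Day 10 | Day 12, unscheduled | 4 |
| Day 7, weekly labs after discharge | Day 14, scheduled | 0 |
| Day 7, weekly labs after discharge | Day 9, unscheduled | 10 |

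**Yield.** The documents give no within-subject variability, so I assume independent lognormal draws around a fixed median m (the true level), with CV 15%, 25% or 35% and s = sqrt(ln(1 + CV²)). Then P(draw > k) = 1 - Φ(ln(k/m)/s). At m = 7:

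| CV | P(draw > 5) | P(draw > 8) | Both of two > 5 | At least one of two > 8 | Both > 5, neither > 8 |
|---|---|---|---|---|---|
| 15% | 0.988 | 0.185 | 0.976 | 0.336 | 0.64 |
| 25% | 0.914 | 0.294 | 0.836 | 0.501 | 0.38 |
| 35% | 0.839 | 0.347 | 0.704 | 0.574 | 0.24 |

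The last column is (P(>5) - P(>8))², for example (0.988 - 0.185)² = 0.64.

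**Extra prompts with no drug effect.** Same model; the measured screening value must be below 5 x ULN; five draws on Days 2 to 14; 400,000 simulated subjects. Probability of at least one consecutive pair above 5 x ULN, at CV 15/25/35%:

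- true 3.2 x ULN: 0.000 / 0.005 / 0.033
- true 4.0 x ULN: 0.017 / 0.113 / 0.208
- true 4.8 x ULN: 0.418 / 0.487 / 0.516

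**The case against.** The strongest reply is that little is lost. The whole list is advisory, so a working criterion would still leave the decision to judgment. A reader might infer that such a rise goes unreviewed, or rests on the investigator alone. The documents do not support that. Section 6.5.5 has the investigator assess all laboratory data, and Section 3.4.1 asks for a check of health status, with laboratory results where applicable, before dosing. The sponsor monitors adverse events and toxicities throughout (Section 3.1). Section 3.4.4 allows dosing to be stopped jointly by investigator and sponsor or on DMC advice, and the best-interests clause is mandatory. What is missing is a number that prompts consideration of stopping.

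Nor is the criterion wholly dead, given the 2.5-day window for a pre-dose rise. Criterion 4 also narrows the gap: it applies from 3 x ULN, exempts no alternative cause, and lists fever and fatigue, which are plausible in COVID-19 inpatients.

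On the remedy, quoting 70-98% as the gain would overstate it. In 34-57% of cases at least one of the two draws already exceeds 8 x ULN. Late confirmations can leave no doses to prevent, and subjects who enter just under 5 x ULN will generate prompts without any drug effect.

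All of this stands and limits the weight of the point. None of it supplies a numeric criterion between 5 and 8 x ULN, or makes the two-week duration fit a two-week course.

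**Conclusion.** The point holds as a minor one: an advisory rule that does not work as written and can be improved cheaply. That a rise beginning on drug cannot meet the two-week criterion within the course, and that no other listed number covers an isolated, asymptomatic 5-8 x ULN value with bilirubin below 2 x ULN and no INR rise, follows from the protocol text and day arithmetic alone.

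The yield of a repaired criterion rests on the assumed CV range and a constant true level, which is a rough model of acute illness. At a true 7 x ULN it would add roughly 24-64% of pairs not already caught by the 8 x ULN criterion.

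A reader might go further and infer a threat to the primary endpoint, or a known number of subjects at risk. The documents support neither: they give no frequency of such rises, and enzyme rises still enter the laboratory and adverse-event summaries (SAP Sections 3.5.1 and 3.5.2). The SAP exposure category beyond 14 days (Section 3.3.8) is a reporting bin and does not authorise longer dosing.

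**What to change.** Replace the second liver criterion in Section 3.4.1 with: *ALT or AST >5 x ULN, confirmed on a repeat draw at least 48 hours later*. Keep it advisory. When the next scheduled draw would leave no doses to prevent (first seen on Day 10, or a discharged subject on weekly labs), confirm with an unscheduled chemistry draw, which Sections 6.5.5 and 6.6 already allow. Repeat confirmation has a precedent in the QTcF entry, although that entry asks for two repeats and this asks for one.

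The cost is a short amendment with IRB/IEC approval (Section 10.3.1), an occasional extra chemistry draw, and extra advisory prompts in subjects entering just under 5 x ULN. Under the assumed CVs these affect about 42-52% of subjects over five draws at a true 4.8 x ULN, 2-21% at 4.0, and at most about 3% at 3.2. None of these prompts compels a stop.

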3.4.2 Subject withdrawal

Subjects may withdraw from the study at any time and for any reason without prejudice to their future medical care by the investigator or at the study site. In all cases of impending consent withdrawal, investigators will be given instructions to meet and discuss with the participant their options of continuing in the study. The investigator should ensure understanding and documentation of the reasons for the participant's desire to withdraw consent. Every effort should be made to keep subjects in the study, including if a subject and/or their treating physician decides to prematurely discontinue study treatment. Unless the participant provides their written withdrawal of consent or there is other written documentation by the investigator confirming the participant's verbal intent to completely withdraw from the trial, participants should be followed for all protocol-specified evaluations and assessments. The reasons for subjects not completing the study will be recorded.

A subject may be withdrawn from the study if he or she is lost to follow-up. For subjects to be considered as lost to follow-up, 2 attempts should be made to contact the subject to return for the scheduled study visit. After 2 attempts, a certified letter should be sent to the subject's address requesting the subject to contact the investigator to schedule a follow-up assessment. If no reply is provided by the subject within 30 days of receipt of the certified letter, the subject can then be considered lost to follow-up.

